Training and Supervision of Research Staff. The UCLA Research Center will provide all study research staff training in specific duties for the PIP study, standard data collection procedures, adverse events reporting, and human subjects and confidentiality issues. The training will be based on a series of training modules provided by ISAP to all of its research staff on standard research topics; additional topics related to the PIP study will also be covered. Interviewers will have worked on other ISAP projects or will have had previous interview experience, but in either case, they will be specially trained for this study. ISAP’s Training Unit and the Project Director will provide a three-day training for interviewers that will consist of (1) an overview of the purpose and design of the study; (2) instruction on the collection of interview and records data, including issues of confidentiality and informed consent; (3) training on administering the ASPD portion of the SCID; (4) observation of sample interviews by the Project Director; and (5) mock interviews with the Project Director using videotape. In addition, interviewers will complete the regular ISAP training required of all interviewers, which includes the following topics: Good Research Practices, Safety Concerns in Dealing with Patients, and Data Collection Procedures. Staff also receive Red Flags training that covers suicide, danger to others, child abuse, elder/dependent adult abuse, and domestic violence (see Appendix B). Project staff are trained to refer those in treatment to the primary counselor or supervising counselor of the treatment agency. For those out of treatment, project staff are trained to use a variety of resources, including a 24-hour on-call clinician. At the completion of training, staff are well-prepared to work with criminally and psychiatrically high-risk populations. Interviewers also complete an annual refresher training on these issues. Interviewers receive a certificate for each training after successfully demonstrating competency (above 80%) on an examination. After initial training, interviewers and the Project Director will confer weekly to exchange information on recruitment or follow-up problems, clarify interview and other data collection procedures, and discuss specific questions.

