vouchers to pay for more expensive activities at the end, or vouchers will be deposited into your Walden House account in order to purchase items of your choice at the end of each week. When you get HIV tested, you can earn a bonus voucher. You will start receiving incentives on the Monday following this interview (you will earn nothing until that day)."

After this brief description of the program, the intake worker should give applicants an opportunity to ask questions. Keep this interaction brief; the research staff can provide more detailed information after the structured baseline interview is completed. If clients so wish, they should then be enrolled in the study and a baseline interview should be conducted or scheduled.

Attendance Phase. As clients from the Admission Phase and all others eligible for the Attendance Phase complete the Walden House intake process, the interviewer will meet with them in a private office to determine whether they wish to participate in the Attendance Phase of the study. Within a week of intake, the interviewer will complete the screening form to determine eligibility for the Attendance Phase, explain the consent form, obtain informed consent, and randomize the clients to the Attendance Incentive group or to the Attendance Information group. The interviewer will also update the locator form. There will be no baseline interview for the Attendance Phase.

BASELINE INTERVIEW PROCEDURES

The baseline interview will be conducted within seven days of enrollment in the study. Baseline interviews will be conducted at the prison substance abuse programs in private offices at SATF or in private rooms at Walden House. Several procedures will be followed to maximize the accuracy and honesty of the responses and to standardize data collection:

- 1) interviews are conducted face-to-face by trained interviewers;
- 2) all subjects in the study will receive \$10 Target gift card payment for participating in research interviews;
- 3) the interview setting is private to minimize distractions and ensure confidentiality;
- 4) participants are reminded of the confidentiality of the information they provide;
- 5) interviewers provide breaks during the interview and are attentive to signs of fatigue;
- 6) interviewers introduce the voucher program and re-cap study procedures (including randomization process and give each client a Client FU Contact Card and, if assigned to the incentive group, a Client Pocket Guide for them to keep);

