For the Admission Phase, the interviewer at SATF will randomize using only the first two items because all subjects leaving from SATF to Walden House Los Angeles will be voluntary SAP graduates. The baseline variables will be entered into the project computers at the project sites using the Urn Randomization Program, and the resulting group assignment will be determined immediately by the interviewer, who will inform the client and Walden House treatment staff of the group to which the client has been assigned. Although there may be disappointment among clients assigned to the Information groups, making it clear to each client that they only have a 50/50 chance of ending up in either group will lessen the possibility of resentment and demoralization during treatment.

A concern in randomized studies is that violations of assignment could occur at the recruitment site and/or after entry into the assigned group. This should not be a problem in the Admission Phase since only one behavior is involved (showing up for treatment). But it might be a problem in the Attendance Phase. The Project Director will monitor the randomization protocol for the Attendance Phase monthly to ensure that the integrity of random assignment is preserved (i.e., there are no crossovers from one group to another). Even though crossovers may still occur, hypothesis tests will be use the analyze-as-assigned principle.

FOLLOW-UP INTERVIEW PROCEDURES

For the 12-month assessment, interviewers will meet with participants at locations that are safe, ensure privacy, and minimize travel costs. If participants are incarcerated, they will be interviewed in jail or prison. If a face-to-face follow-up interview is not feasible (e.g., client located out of state), the interview will be conducted by telephone.

INTERVENTION MONITORING, QUALITY ASSURANCE AND FEEDBACK

Meetings and Communication. Regular communication between treatment staff and research staff will be critical to ensure uniformity of implementation of the PIP protocol. The primary contact for case managers is the project director, [name]. If, based on shared experiences, the protocol requires modification; all participating staff will receive formal written notification from UCLA-ISAP.

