Client Satisfaction Questionnaire (CSQ). At the 12-month assessment, participants will complete the CSQ to rate their satisfaction with the services that they have received using a four-point Likert-type scale (with the response categories based on the specific question). The CSQ has high levels of internal consistency and consumer acceptability. Cronbach's alpha is .86. High correlations have been found with other health consumer satisfaction instruments (from .60 to .80) (Attkisson & Greenfield, 1994). An item will be added asking whether participants were satisfied with their initial assignment to assess for the possibility of resentful demoralization over the group assignment that they received (Shadish, Cook, & Campbell, 2002).

Sustainability. A key issue in implementation is whether interventions found to be effective are—or at least can be—sustained by treatment providers using their own resources (Mancini &

Marek, 2004; Miller et al., 2003; O'Loughlin et al., 1998). After the CM intervention is completed, treatment staff will be asked whether the intervention can be continued once research support is withdrawn. Their views will be obtained from a focus group (see below) and from the Dimensions of Sustainability Questionnaire (O'Loughlin et al., 1998). This brief questionnaire, based on an instrument developed for community programs, contains 15 questions on staff perceptions of the sustainability of an intervention.

6. *Qualitative Assessment*

Qualitative data will consist of notes from monthly project meetings and transcriptions of audio recordings from the CM Information Session, the Intervention Development Workgroups, and from focus groups conducted after the end of the CM intervention. The focus groups will be conducted with clients and with Walden House program directors and staff (separately) to assess satisfaction with the CM intervention, to determine their views of the utility of CM in the residential treatment environment, to elicit views on research-to-practice issues, and, for staff, to ask about plans to continue use of CM techniques after research implementation is completed, including issues of cost. In addition, staff and clients will be asked whether it appeared that clients were dissatisfied with their assigned treatment and whether this affected their participation in the study.

DATA COLLECTION PROCEDURES

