Interview Procedures. The baseline interview will be conducted within seven days of enrollment in the study. Baseline interviews will be conducted at the prison substance abuse programs in private offices at SATF. For the 12-month assessment, interviewers will meet with participants at locations that are safe, ensure privacy, and minimize travel costs. If participants are incarcerated, they will be interviewed in jail or prison. If a face-to-face follow-up interview is not feasible (e.g., client located out of state), the interview will be conducted by telephone. Several procedures will be followed to maximize the accuracy and honesty of the responses and to standardize data collection: (1) interviews are conducted face-to-face by trained interviewers; (2) the interview setting is private to minimize distractions and ensure confidentiality; (3) participants are reminded of the confidentiality of the information they provide; (4) interviewers provide breaks during the interview and are attentive to signs of fatigue; (5) interviewers look for reporting inconsistencies and socially desirable responses; and (6) consistency checks on reporting are built in as part of the interview process. The Project Director will periodically sit in on interviews to ensure compliance with interview protocols and to identify problems that need correction. As a quality check, the Project Director will randomly call 10% of participants for whom interview forms are on file to verify that the interview took place and to ask about suggestions on interview procedures (see ISAP's data integrity policy in Appendix C).

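### The 12-month interviewers are neither masked to arm nor separated from those who randomize, and the assignment-satisfaction item does not say which of two assignments it means

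*Protocol*

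**What the plan says.** - **Assignment.** In the Protocol, Randomization, the urn program is run on the project computers and "the resulting group assignment will be determined immediately by the interviewer, who will inform the client and Walden House treatment staff of the group". For the Attendance Phase (Recruitment - Intake Procedures), the interviewer is to "randomize the clients to the Attendance Incentive group or to the Attendance Information group".
- **Staffing.** Under Training Procedures, "interviewers and the Project Director will confer weekly to exchange information on recruitment or follow-up problems".
- **Follow-up.** Under Data Collection Procedures, Interview Procedures: "For the 12-month assessment, interviewers will meet with participants at locations that are safe, ensure privacy, and minimize travel costs". The measures listed there to standardize data collection include that "interviewers look for reporting inconsistencies and socially desirable responses". Under Data Entry, Quality Control, and Data Security, the interviewer edits the recorded answers, consistency being one of the criteria, and a flagged error may go back to the original interviewer.
- **Assignment item.** Under Data Sources, Treatment: "At the 12-month assessment, participants will complete the CSQ to rate their satisfaction with the services that they have received". The protocol then adds: "An item will be added asking whether participants were satisfied with their initial assignment". The stated purpose is to detect resentful demoralization, and Design Analyses relies on the questionnaire, together with focus groups, to judge whether the findings are biased by it.

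**The concern.** Where an outcome is what a client tells an interviewer, the interviewer's knowledge of the arm can affect how an answer is queried, recorded or edited. If that differs between arms, it creates a group difference that has nothing to do with the vouchers. Where no objective measure stands beside the answer, an analysis plan cannot take it out afterwards. At stake are the 12-month claims on abstinence (H5), psychosocial functioning (H7), HIV risk (H8) and use of HIV services (H9).

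The assignment item raises a second, smaller matter. Some men in the Attendance comparison have been randomized once and others twice. If the two kinds of participant answer about different assignments, the demoralization check loses its meaning for the comparison it is needed for.

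**Working it through.** The protocol gives no figure on this point, so there is none to reproduce. The check is mainly a reading of the text, followed by an illustration of scale.

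**1. Who knows the arm at follow-up.** H5 and H7 to H9 compare the Attendance arms, so the assignment that matters is the one made at Walden House. An interviewer makes it. The Training section treats interviewers as one group dealing with both recruitment and follow-up. The follow-up sections name interviewers again, without masking or separation. In Table 3, Attendance randomization runs in months 8-33 and follow-up interviews in months 26-51, so the two overlap in months 26-33. The Project Director, who sits in on interviews, also monitors Attendance randomization, so that oversight is not arm-blind.

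**2. Which outcomes are exposed.**

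| Outcome | Source | Exposed? |
|---|---|---|
| Admission, retention (primary) | Program records | No |
| H6 arrest, reincarceration | State records | No |
| H5 abstinence | Self-report or positive urine | In part |
| H7 psychosocial | Self-report, CJ-DATS form and BSI | Yes |
| H8, H9 HIV risk and services | Self-report | Yes |

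For H5, a positive specimen settles the matter whatever the client says. But the specimen is voluntary (Participant Reimbursement) and is not taken in jail or prison (Drug Testing). In those cases the client's answer alone decides.

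**3. What a shift would do.** Inputs:
- 170 at follow-up (Power Analysis), hence 170/2 = 85 per arm with equal allocation.
- Two-sided .05 (Hypothesis Testing).
- Assumed: 50% abstinent in both arms, no true effect, and a net shift δ in one arm's recorded answers.

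SE = √(2 × 0.5 × 0.5 / 85) = 0.0767.

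Rejection probability = Φ(−1.96 + δ/SE) + Φ(−1.96 − δ/SE).

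- δ = 0: .05.
- δ = 0.05: δ/SE = 0.652; Φ(−1.308) + Φ(−2.612) ≈ .10.
- δ = 0.10: δ/SE = 1.304; Φ(−0.656) + Φ(−3.264) ≈ .26.

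With a base rate anywhere from 40% to 60%, a two-proportion calculation gives about .10 for 5 points and .26 to .28 for 10 points. For a continuous scale, assumed shifts of 0.1 and 0.2 SD give about .10 and .26.

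**4. Where the assignment item falls.** Its position relative to the outcome items is not stated. The follow-up times in Table 4 add to 45 + 15 + 10 + 5 = 75 minutes with the satisfaction questionnaire and 65 without it. Both fit the stated 1.0 to 1.5 hours, so the times do not settle whether it is given within the same interview.

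**5. Which assignment is meant.** Admission Phase clients who arrive at Walden House are re-randomized (Randomization). Others enter only at the Attendance Phase. Read literally, the initial assignment is the Admission arm for the first group and the Attendance arm for the second.

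**The case against.** The case on the other side removes several stronger readings that a reader might infer.

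- **That interviewers are told to probe.** The text has them look for such answers and gives no probing step. Items are close-ended and consistency checks are built in, which narrows discretion. What stands is that neither the response to a suspect answer nor the later editing has an arm-neutral rule.
- **That the person who randomized a man also interviews him at 12 months.** The protocol does not say so. It only fails to prevent it, and the two activities overlap for eight of the scheduled months.
- **That the satisfaction item unmasks the interviewer.** Participants complete the questionnaire, and being satisfied or not does not identify an arm. It could matter only if it came before the outcome items and the interviewer saw or heard the reply. The instruments are not in the text at hand, so the order cannot be judged.
- **That H5 rests on self-report alone.** A positive urine counts as use, and clients are told at the start of the interview that a specimen will be requested. This protection is real but partial.
- **That the item is useless as a demoralization check.** Its stated purpose concerns the assignment received, its final wording is not shown, and focus groups also cover dissatisfaction. The wording is ambiguous for re-randomized men, no more.

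It is also fair that the shifts used above have no basis in the documents.

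**Conclusion.** The concern holds in a limited form. If the plan is followed as written, nothing keeps the Attendance arm from the person who collects and edits the 12-month self-reports. This is a gap in conduct, not evidence that bias will occur. The false-positive figures of about .10 and .26 rest on assumed net shifts of 5 and 10 points, all in one direction, and on an assumed 50% abstinence rate. They show sensitivity and do not predict bias.

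The ambiguity of the assignment item is a separate and lesser point, confined to men randomized in both phases. The trial's main conclusions on admission and retention are untouched. The changes are worth making because they are cheap and because these matters are settled in the field, before any analysis.

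**What to change.** 1. Keep the arm off the follow-up case file. Where existing staffing allows, give each 12-month interview to an interviewer who did not randomize or brief that client.
2. Place the satisfaction questionnaire and its assignment item after all outcome items and the urine specimen.
3. Give fixed, neutral wording for any follow-up question on an inconsistent or doubtful answer, and apply the same editing rule in both arms.
4. Name the assignment in the item. Ask separately about the Admission and the Attendance assignment, and use the latter for the demoralization check on the Attendance comparison.

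The cost is a change of form order, a few lines of interviewer instruction and some constraint on scheduling. No added sample is needed. Some clients will reveal their arm anyway, so the exposure is reduced and not removed.
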